10.1.13.1 Absorption and Distribution

Following oral administration, sorafenib reaches peak plasma levels in approximately 3 hours. When given with a moderate-fat meal (30% fat; 700 calories), bioavailability was similar to that in the fasted state. With a high-fat meal (50% fat; 900 calories), sorafenib bioavailability was reduced by 29% compared to administration in the fasted state. It is recommended that sorafenib be administered without food. Mean C_{max} and AUC increased less than proportionally beyond doses of 400 mg administered orally twice daily. In vitro binding of sorafenib to human plasma proteins is 99.5%.

10.1.13.2 Metabolism and Elimination

Sorafenib is metabolized primarily in the liver, undergoing oxidative metabolism, mediated by CYP3A4, as well as glucuronidation mediated by UGT1A9. Sorafenib accounts for approximately 70-85% of the circulating analytes in plasma at steady-state. Eight metabolites of sorafenib have been identified, of which five have been detected in plasma. The main circulating metabolite of sorafenib in plasma, the pyridine N-oxide, shows in vitro potency similar to that of sorafenib. This metabolite comprises approximately 9-16% of circulating analytes at steady-state. Following oral administration of a 100 mg dose of a solution formulation of sorafenib, 96% of the dose was recovered within 14 days, with 77% of the dose excreted in feces, and 19% of the dose excreted in urine as glucuronidated metabolites. Unchanged sorafenib, accounting for 51% of the dose, was found in feces but not in urine.

10.1.13.3 Special Populations

Age: Analyses of demographic data suggest that no dose adjustments are necessary for age.

Gender: Analyses of demographic data suggest that no dose adjustments are necessary for gender.

Race: A study of the pharmacokinetics of sorafenib indicated that the mean AUC of sorafenib in Asians (N=78) was 30% lower than in Caucasians (N=40).

Pediatric: There are no pharmacokinetic data in pediatric patients.

Hepatic Impairment: Sorafenib is cleared primarily by the liver. Comparison of data across studies suggests that in HCC patients with mild (Child-Pugh A) or moderate (Child-Pugh B) hepatic impairment, 400 mg doses of sorafenib appear to be associated with AUC values that were 23 to 65% lower than those of other subjects without hepatic impairment. The AUC of sorafenib is similar between HCC patients with mild (Child-Pugh A) and moderate (Child-Pugh B) hepatic impairment. The pharmacokinetics of sorafenib have not been studied in patients with severe (Child-Pugh C) hepatic impairment.

Renal Impairment: In a study of drug disposition after a single oral dose of radiolabeled sorafenib to healthy subjects, 19% of the administered dose of sorafenib was excreted in urine. In a clinical pharmacology study, the pharmacokinetics of sorafenib were evaluated following administration of a single 400 mg dose to subjects with normal renal function, and in subjects with mild (CrCl > 50-80 ml/min), moderate (CrCl 30-50 ml/min), or severe (CrCl <30 ml/min) renal impairment, not undergoing dialysis. There was no relationship observed between sorafenib exposure and renal function. No dosage adjustment is necessary based on mild, moderate or severe renal impairment not undergoing dialysis. Monitoring of fluid balance and electrolytes in patients at risk of renal dysfunction is advised.

10.1.14 Administration:

400 mg (2 tablets) orally twice daily without food (at least 1 hour before or 2 hours after a meal).

10.1.15 Supplier:

Bayer Pharmaceuticals

10.1.16 Unused or defective agent:

Refer to the detailed instructions described in Section [10.2.18](#) Unused or defective drug will be destroyed. Bayer Pharmaceuticals should be notified of this action.

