2.4 TREATMENT ASSIGNMENT AND DESCRIPTIVE FACTORS

Patients with recurrent malignant glioma will be enrolled into one of the following groups. Accrual goals and endpoints for each group are determined separately as described in the statistical section.

There will be an accrual of approximately 3-6 eligible patients per dose level to the Phase I component of the study. Patients removed at any time for toxicity are evaluable. Phase I patients removed from study treatment within 28 days for reasons other than toxicity may be replaced.

Cohorts

Number	Name	Description
1	Phase 1 (closed)	Patients with Glioblastoma or Anaplastic Glioma
2A	Phase 2 Group A (closed)	Patients with Glioblastoma with NO prior bevacizumab exposure
2B	Phase 2 Group B	Patients with Glioblastoma with PRIOR bevacizumab exposure
2C	Phase 2 Group C (closed)	Patients with Anaplastic Glioma with NO prior exposure to bevacizumab (Grade III Glioma Group)

Arms

Number	Name	Description
1	Phase 1 (closed)	Combination of sorafenib (7 days on, 7 days off) and everolimus daily over a 28-day cycle at escalating doses

2	Phase 2	Combination of sorafenib (7 days on, 7 days off) and everolimus daily over a 28-day cycle: Sorafenib 400 mg BID PO (days 1-7 and days 15-21) Everolimus 5 mg PO daily (days 1-28)
---	---------	---

There will be a total accrual of approximately 82 eligible patients to the Phase II study (34 recurrent GBM with no prior exposure to bevacizumab, 16 recurrent Anaplastic Glioma with no prior exposure to bevacizumab, and 32 glioblastoma with prior exposure to bevacizumab).

Subjects in Cohort 1 were directly assigned to Arm 1.

Subjects in Cohorts 2A, 2B and 2C will be directly assigned into Arm 2.

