3.1.2 Dose Escalation

Patients will be treated at the dose levels in Table 3-11 starting at dose level 1. Initially everolimus and sorafenib will be administered continuously. If two DLTs are encountered at the first dose level (sorafenib 400 mg twice daily and everolimus 5 mg daily) the dose for the next cohort of patients will be decreased to sorafenib 400 mg twice daily 7 days on, 7 days off and everolimus 5 mg daily (dose level -1). If dose level -1 is tolerated, dose escalations will occur along the “b” pathway (-1, 1b, 2b, 3b, 4b).

If two DLTs are encountered at dose level 2, the dose for the next cohort of patients will be reduced to sorafenib 400 twice daily, 7 days on 7 days off and everolimus 7.5 mg daily (dose level 1b). Subsequent dose escalations will occur along the “b” pathway (2, 1b, 2b, 3b, 4b).

The study drugs will be self-administered (by the patients themselves). The investigator will instruct the patient to take the study drug exactly as specified in the protocol. Patients will be instructed to take the study drugs in the morning, at the same time each day.

The study drugs must be taken 1 hour before or two hours after food. Consumption of grapefruit juice should be avoided while taking the study drugs. If vomiting occurs, no attempt should be made to replace a dose.

All dosages prescribed and dispensed to the patient and all dose changes during the study must be recorded.

Table 3-1: Phase I dosing table.

DOSE LEVEL	SORAFENIB	EVEROLIMUS
-1	400 mg BID,	5 mg daily

DOSE LEVEL	SORAFENIB	EVEROLIMUS
	7 days on 7 days off	
1	400 mg BID	5 mg daily
2	400 mg BID	7.5 mg daily
3	400 mg BID	10 mg daily
4	600 mg BID	10 mg daily
1b	400 mg BID, 7 days on 7 days off	7.5 mg daily
2b	400 mg BID, 7 days on 7 days off	10 mg daily
3b	600 mg BID, 7 days on 7 days off	10 mg daily
4b	800 mg BID, 7 days on 7 days off	10 mg daily

Note: On the sorafenib 7 days on 7 days off schedule, sorafenib will be given on days 1-7 and 15-21.

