3.2 PHASE II STUDY DESIGN

3.2.1 Drug Administration

All patients treated on the phase II cohorts will receive a combination of sorafenib (7 days on, 7 days off) and everolimus daily over a 28-day cycle, as follows:

Sorafenib 400 mg BID PO (days 1-7 and days 15-21)

Everolimus 5 mg PO daily (days 1-28)

There is not a defined set of maximum number of cycles that a patient may have. Patients may continue with protocol therapy until criteria for “Off Treatment” is met. See Section **3.7.1**.

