3.3.1 Within Treatment Cycles

If a patient experiences toxicities during a treatment cycle, the treatment will be immediately suspended until a grade 1 or less toxicity. If the toxicity resolves to less than or equal to grade 1 within 2 weeks, the patient will be retreated at the dose level described in Table **3-2** below. (Refer to Table **3-6** and Table **3-7** for management of everolimus-induced toxicities and Table **3-8**, Table **3-9** and Table **3-10** for management of sorafenib-induced toxicities.) If toxicity persists, the patient should be taken off study.

Two dose reductions are permitted. Doses that are reduced for sorafenib or everolimus related toxicity will not be re-escalated, even if there is minimal or no toxicity with the reduced dose. Patients whose dose has been reduced for adverse events that are subsequently not felt to be related to sorafenib or everolimus may have the dose re-escalated after completion of one cycle with toxicities less than or equal to grade 1. If any patient has further toxicities that would require additional reductions, or if treatment is held for more than 2 consecutive weeks because of ongoing

toxicity, the Study PI will assess if the patient should remain in the study (if the patient has benefited from treatment).

Table 3-2: Dose Modification Table

DOSE LEVEL	SORAFENIB	EVEROLIMUS
1 (starting dose)	400 mg BID 7 days on 7 days off	5 mg daily
-1	400 mg AM dose 200 mg PM dose 7 days on 7 days off	5 mg daily
-2	200 mg AM dose 200 mg PM dose 7 days on 7 days off	5 mg daily

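### The sorafenib schedule is stated inconsistently: section 10.1.14 gives no dosing days, the phase I arm description conflicts with section 3.1.2, and a morning-only instruction does not fit twice-daily dosing

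*Combined protocol and SAP*

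**What the plan says.** **Phase II.** Section 3.2.1 gives "Sorafenib 400 mg BID PO (days 1-7 and days 15-21", and section 2.4 repeats this for Arm 2. The starting row of Table 3-2 reads "400 mg BID 7 days on 7 days off". In section 13.5, the pill diary prints days 8-14 and 22-28 as off days and has AM and PM columns. The pill count form also carries twice-daily dosing on the 7-on/7-off schedule.

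**Drug information.** Section 10.1.14, headed Administration, gives "400 mg (2 tablets) orally twice daily without food (at least 1 hour before or 2 hours after a meal". It names no days and does not refer to section 3.

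**Phase I.** Section 2.4 describes Arm 1 as "Combination of sorafenib (7 days on, 7 days off) and everolimus daily over a 28-day cycle at escalating doses". Section 3.1.2 says "Initially everolimus and sorafenib will be administered continuously" and describes the "first dose level (sorafenib 400 mg twice daily and everolimus 5 mg daily". Table 3-1 lists levels 1 to 4 with no off-weeks, and levels -1 and 1b to 4b with them. Its note defines the intermittent schedule: "On the sorafenib 7 days on 7 days off schedule, sorafenib will be given on days 1-7 and 15-21".

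**Time of day.** Section 3.1.2 also says: "Patients will be instructed to take the study drugs in the morning, at the same time each day".

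**The concern.** A protocol should give one regimen wherever a reader looks for it. Here a reader who consults only the sorafenib pharmaceutical section finds a dose and a frequency but no off-weeks. That is the form in which Table 3-1 writes its continuous levels. If the text were followed literally in phase II, the patient would receive a schedule other than the one whose progression-free survival rate is being estimated, and the toxicity counted in the first 28-day cycle would belong to that other schedule.

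The Arm 1 label raises a reporting problem. If phase I results were summarised under it, events on continuous levels would appear to have arisen on intermittent dosing. The combination's safety would then be described for a schedule that those patients did not receive.

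The morning instruction is a smaller matter of the same kind. As worded, it covers both drugs and leaves no place for the second daily sorafenib dose.

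**Working it through.** The plan states no sorafenib total per cycle, so there is no figure of its own to reproduce. The check is dose arithmetic followed by a comparison of the texts.

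**Inputs**
- Tablet strength: 200 mg (section 10.1.6).
- Dose: 400 mg twice daily (sections 3.2.1 and 10.1.14).
- Cycle length: 28 days (section 3.2.1).
- Dosing days on the intermittent schedule: 1-7 and 15-21, so 7 + 7 = 14 (section 3.2.1 and the note to Table 3-1).

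**Formula**

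Total per cycle = mg per dose × doses per day × dosing days. Tablets = total ÷ 200.

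- Any dosing day, under either text: 400 × 2 = 800 mg = 4 tablets.
- Section 3.2.1: 800 × 14 = 11,200 mg = 56 tablets.
- Section 10.1.14, assuming that no stated days means every day: 800 × 28 = 22,400 mg = 112 tablets.
- Ratio per cycle: 22,400 ÷ 11,200 = 2.0. Ratio per dosing day: 800 ÷ 800 = 1.0.

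**Is every day a fair reading of 10.1.14?** The same formula applied to Table 3-1 shows the protocol's own notation:

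| Level | Sorafenib as written | Dosing days | mg per cycle |
|---|---|---|---|
| 1, 2, 3 | 400 mg BID | 28 | 22,400 |
| 4 | 600 mg BID | 28 | 33,600 |
| -1, 1b, 2b | 400 mg BID, 7 on/7 off | 14 | 11,200 |
| 3b | 600 mg BID, 7 on/7 off | 14 | 16,800 |
| 4b | 800 mg BID, 7 on/7 off | 14 | 22,400 |

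In this table a bare twice-daily dose means continuous dosing, and the intermittent rows always carry the qualifier. Section 10.1.14 has no qualifier, so the continuous reading is a natural one, though not the only one.

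**Arm 1.** Section 2.4 applies 7 on/7 off to all of phase I. Section 3.1.2 and Table 3-1 have four continuous levels, and the escalation begins on the continuous path. This conflict does not depend on reading anything into silence.

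**Time of day.** The tables in section 3 give sorafenib twice daily, the reduced level -1 in Table 3-2 splits AM and PM doses, and the diary has both columns. The sentence in 3.1.2 names only the morning. I put no figure on this, because the text does not say how a patient would resolve it.

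**The case against.** The strongest reply is that section 10.1.14 is drug information and does not define the trial regimen. Its dose per intake and per dosing day agrees with section 3.2.1, and it is silent on days. The matching everolimus entry, 10.2.14, gives no dose at all, which suggests that these entries describe how to take a drug. The 2-fold figure therefore rests on reading silence as every day. That stands as a limit on the claim. It does not remove the point, because 10.1.14 does restate a dose and frequency, and Table 3-1 writes continuous dosing in the same way.

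It is also fair that the exposure is small. Section 2.4 marks phase I and Groups A and C as closed. Section 9.4 says that subjects at non-NCI sites were off treatment at the time of Amendment C. DLTs are judged by dose level or combination (sections 3.1.2 and 7.1) and not by arm label, so misattribution is a risk in reporting, not a fault in the escalation rule.

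A reader might infer more than the documents support:

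- **That 10.1.14 governs dispensing.** No section gives it that role. The pill count form, which records tablets dispensed, carries 7 on/7 off.
- **That 10.1.14 is the only administration instruction.** Sections 3.1.1 and 3.2.1 are both headed Drug Administration.
- **That 10.1.14 describes dose level 1.** It does not mention everolimus. Read as continuous, its sorafenib dose fits levels 1, 2 and 3 of Table 3-1 equally, and level 1 of Table 3-2 is the intermittent regimen. The match to level 1 of Table 3-1 appears only if everolimus 5 mg is added from elsewhere.
- **That 10.1.14 states a regimen already found too toxic.** The phase II regimen equals level -1 of Table 3-1, and section 3.1.2 describes a move to that level after two DLTs at level 1. But the documents report no DLT counts, so this would be an inference from the rule and not a finding.

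**Conclusion.** The point holds as an inconsistency in the protocol text, in three places:

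1. Section 10.1.14 omits the dosing days. On the assumption that it means every day, it gives twice the sorafenib per 28-day cycle of section 3.2.1.
2. The Arm 1 description in section 2.4 conflicts directly with section 3.1.2 and Table 3-1.
3. The morning instruction in section 3.1.2 does not fit a twice-daily drug.

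The seriousness is modest. The patient-facing and dispensing forms agree with section 3.2.1, and phase I is closed. No sample size, power or error rate changes. Which schedule is right is for the sponsor to say.

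**What to change.** The sponsor should reconcile three sets of passages:

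- section 10.1.14 with section 2.4 (Arm 2), section 3.2.1 and Table 3-2;
- the Arm 1 description in section 2.4 with section 3.1.2 and Table 3-1;
- the morning instruction in section 3.1.2 with twice-daily sorafenib.

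Once they are reconciled, state the schedule in one place and cross-refer to it from the others. Report phase I toxicity by dose level and by the schedule actually given, not by arm label alone.

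The cost is a wording amendment. No data collection changes, since section 3.1.2 already requires the doses prescribed and dispensed, and all dose changes, to be recorded.

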10.2 EVEROLIMUS

10.2.1 Drug Name:

Everolimus

10.2.2 Chemical Name:

(1R,9S,12S,15R,16E,18R,19R,21R,23S,24E,26E,28E,30S,32S,35R)-1,18- dihydroxy-12-{(1R)-2-[(1S,3R,4R)-4-(2-hydroxyethoxy)-3-methoxycyclohexyl]-1-methylethyl}-19,30-dimethoxy-15,17,21,23,29,35-hexamethyl-11,36-dioxo-4-aza-tricyclo[30.3.1.04,9]hexatriaconta-16,24,26,28-tetraene-2,3,10,14,20-pentaone.

10.2.3 Molecular Formula:

C₅₃H₈₃NO₁₄

10.2.4 Molecular Weight:

958.2

10.2.5 Appearance:

- 2.5 mg tablet White to slightly yellow, elongated tablets with a beveled edge and no score, engraved with “LCL” on one side and “NVR” on the other.
- 5 mg tablet - White to slightly yellow, elongated tablets with a beveled edge and no score, engraved with “5” on one side and “NVR” on the other.
- 7.5 mg tablet White to slightly yellow, elongated tablets with a beveled edge and engraved with “7P5” on one side and “NVR” on the other.
- 10 mg tablet - White to slightly yellow, elongated tablets with a beveled edge and no score, engraved with “UHE” on one side and “NVR” on the other.

10.2.6 How supplied:

Each carton contains 4 blister cards of 7 tablets per card, total 28 tablets per carton.

Store everolimus tablets at 25° C (77°F); excursions permitted between 15°–30°C (59°–86°F). [See USP Controlled Room Temperature.] Store in the original container, protect from light and moisture. Keep this and all drugs out of the reach of children. Procedures for proper handling and disposal of anticancer drugs should be considered. Everolimus tablets should not be crushed. Direct contact of crushed tablets with the skin or mucous membranes should be avoided. If such contact occurs, wash thoroughly. Personnel should avoid exposure to crushed tablets.

10.2.7 Formulation:

Everolimus is supplied as tablets for oral administration containing everolimus together with butylated hydroxytoluene, magnesium stearate, lactose monohydrate, hypromellose, crospovidone and lactose anhydrous as inactive ingredients.

10.2.8 Storage and Stability:

Current stability data permits a shelf-life of 36 months at storage conditions below 30°C and maintenance in the original packs.

10.2.9 Mechanism of Action:

Everolimus is an inhibitor of mTOR (mammalian target of rapamycin), a serine-threonine kinase, downstream of the PI3K/AKT pathway. The mTOR pathway is dysregulated in several human cancers. Everolimus binds to an intracellular protein, FKBP-12, resulting in an inhibitory complex formation and inhibition of mTOR kinase activity. Everolimus reduced the activity of S6 ribosomal protein kinase (S6K1) and eukaryotic elongation factor 4E-binding protein (4E-BP), downstream effectors of mTOR, involved in protein synthesis. In addition, everolimus inhibited the expression of hypoxia-inducible factor (e.g., HIF-1) and reduced the expression of vascular endothelial growth factor (VEGF). Inhibition of mTOR by everolimus has been shown to reduce cell proliferation, angiogenesis, and glucose uptake in in vitro and/or in vivo studies.

10.2.10 Pharmacology:

10.2.10.1 Drug Interactions

Everolimus is a substrate of CYP3A4, and also a substrate and moderate inhibitor of the multidrug efflux pump Pgp. In vitro, everolimus is a competitive inhibitor of CYP3A4 and a mixed inhibitor of CYP2D6.

10.2.10.1.1 Agents that may Increase Everolimus Blood Concentrations

CYP3A4 Inhibitors and Pgp Inhibitors: In healthy subjects, compared to everolimus treatment alone there were significant increases in everolimus exposure when everolimus was co-administered with:

- ketoconazole (a strong CYP3A4 inhibitor and a Pgp inhibitor) - Cmax and AUC increased by 3.9- and 15.0-fold, respectively.
- erythromycin (a moderate CYP3A4 inhibitor and a Pgp inhibitor) - Cmax and AUC increased by 2.0- and 4.4-fold, respectively.
- verapamil (a moderate CYP3A4 inhibitor and a Pgp inhibitor) - Cmax and AUC increased by 2.3- and 3.5-fold, respectively.

Concomitant strong or moderate inhibitors of CYP3A4 and Pgp inhibitors should not be used.

10.2.10.1.2 Agents that may Decrease Everolimus Blood Concentrations

CYP3A4 Inducers: In healthy subjects, co-administration of everolimus with rifampin, a strong inducer of CYP3A4, decreased everolimus AUC and Cmax by 64% and 58% respectively, compared to everolimus treatment alone. Consider a dose increase of everolimus when co-administered with strong inducers of CYP3A4 or Pgp if alternative treatment cannot be administered.

Agents whose Plasma Concentrations may be Altered by Everolimus Studies in healthy subjects indicate that there are no clinically significant pharmacokinetic interactions between everolimus and the HMG-CoA reductase inhibitors atorvastatin (a CYP3A4 substrate) and pravastatin (a non-CYP3A4 substrate) and population pharmacokinetic analyses also detected no influence of simvastatin (a CYP3A4 substrate) on the clearance of everolimus.

Patients will be instructed not to take any additional medications (including over-the-counter products) during the course of the study without prior consultation with the investigator. At each visit, the investigator will ask the patient about any new medications he/she is or has taken after the start of the study drug.

All Concomitant medications/Significant non-drug therapies taken \leq 30 days prior to start and after start of study drug, including physical therapy and blood transfusions, should be recorded.

- Growth factors (e.g. G-CSF, GM-CSF, erythropoietin, platelets growth factors etc.) are not to be administered prophylactically but may be prescribed by the investigator for rescue from severe hematologic events, if this is thought to be appropriate.
- Concurrent administration of everolimus and strong CYP3A4 inhibitors (such as ketoconazole, itraconazole, ritonavir) and inducers (such as rifampin, rifabutin) should be

avoided. Provided there is no alternative treatment available, patients should be closely monitored for potential toxicities.

- Concurrent administration of everolimus and moderate CYP3A4 inhibitors (such as erythromycin, fluconazole, calcium channel blockers, benzodiazepines) and moderate CYP3A4 inducers (e.g. carbamazepine, phenobarbital) should also be avoided if possible, or used subject to caution (e.g. increased frequency of safety monitoring, temporary interruption of everolimus).
- Competitive inhibition could occur when everolimus is combined with drugs which are also CYP3A4 substrates. Therefore caution should be exercised in such cases.
- Co-administration with substrates, inducers, or inhibitors of P-glycoprotein should be avoided, if possible, or used subject to caution (e.g. increased frequency of safety monitoring, temporary interruption of everolimus).
- Grapefruit and grapefruit juice affect cytochrome P450 and P-glycoprotein activity and should therefore be avoided.
- In addition, patients should avoid Seville oranges and star fruit, as well as the juice of these fruits, which are potent CYP3A4-inhibitors.
- No chronic treatment with immunosuppressive agents. Topical or inhaled corticosteroids are allowed.
- Everolimus may affect the response to vaccinations making the response to the vaccination less effective. Live vaccines should be avoided while a patient is treated with everolimus.

Oral anticoagulants such as warfarin are CYP2C9 substrates and, as such, no interaction with everolimus is expected. However, drug-drug interaction studies between macrolide antibiotics and warfarin have produced mixed outcomes and the disparity in these findings has led to the conclusion that multiple factors may alter the clearance of warfarin. The co-administration of everolimus and oral anticoagulants is possible but should be subject to verification of coagulation (INR) once steady state is reached (after one week's treatment).

Examples are provided in [Table 3-3](#). A comprehensive list of cytochrome P450 isoenzymes and CYP3A4 inhibitors, inducers, and substrates can be found at <http://medicine.iupui.edu/flockhart>. This website is continually revised and should be checked frequently for updates.

10.2.11 Pre-clinical Toxicology:

In safety pharmacology studies, Everolimus was devoid of relevant effects on vital functions including the cardiovascular, respiratory and nervous systems. Everolimus had no influence on QT interval prolongation. Furthermore, everolimus showed no antigenic potential. Although everolimus passes the blood-brain barrier, there was no indication of relevant changes in the behavior of rodents, even after single oral doses up to 2000mg/kg or after repeated administration at up to 40 mg/kg/day. Based on these findings, the potential of everolimus to affect vital functions in patients is considered to be low. Everolimus is considered to have no genotoxicity or carcinogenicity potential. All significant adverse events observed in preclinical toxicology studies with everolimus in mice, rats, monkeys and minipigs were consistent with its anticipated pharmacologic action as an antiproliferative and immunosuppressant and at least in part reversible after a 2- or 4-week recovery period with the exception of the changes in male reproductive organs,

most notably testes. Ocular effects (lenticular disorders) observed in rats were not observed in any other species and are considered to be a species-specific disorder.

10.2.12 Human Toxicity:

Hypersensitivity to the active substance, to other rapamycin derivatives, or to any of the excipients. Hypersensitivity reactions manifested by symptoms including, but not limited to, anaphylaxis, dyspnea, flushing, chest pain, or angioedema (e.g., swelling of the airways or tongue, with or without respiratory impairment) have been observed with everolimus and other rapamycin derivatives.

WARNINGS AND PRECAUTIONS

